2.4. Secondary Endpoints

The secondary endpoints of this study are:

- Number and rate of patients in clinical remission at Week 8, per each intervention/treatment group. Clinical remission, based on the Mayo Scoring system, is defined as stool frequency subscore = 0 or 1 and rectal bleeding subscore = 0 and endoscopy subscore = 0 or 1 (modified to exclude friability).

- Combined number and rate of patients in clinical remission at Week 8 and at Week 16, per each intervention/treatment group.
- Number and rate of patients with clinical response at Week 8 and Week 16 per intervention/treatment group. Clinical Response is defined as a reduction in Mayo Score of at least 2 points and greater than or equal to 30 percent from baseline with an accompanying decrease in rectal bleeding sub-score of greater than or equal to 1 point or absolute rectal bleeding sub-score of less than or equal to 1 point.
- Number and rate of patients with endoscopic improvement, by segment, and number and rate of patients with endoscopic remission, by segment, at Week 8 and at Week 16 (if available) per intervention/treatment group. Endoscopic improvement is defined as a Mayo endoscopic sub score of ≤1 (excluding friability) and endoscopic remission defined as sub score of 0.
- Number and rate of patients with mucosal healing. Mucosal healing is defined as both endoscopic remission and histological remission (Geboes score < 2.0).
- Reduction relative to baseline in stool and rectal bleeding frequency at every study visit by ABX464 dose group and versus placebo.
- Reduction relative to baseline in partial Modified Mayo Score at every study visit and Modified Mayo Score at Week 16 (if available) by ABX464 dose group and versus placebo.
- Reduction relative to baseline in fecal calprotectin and CRP levels at Week 8 and Week 16 by intervention/treatment group.
- Change relative to baseline in miRNA-124 expression in rectal/sigmoidal biopsies at Week 8 and Week 16 (if available) and in total blood at every timepoints by intervention/treatment group.
- The scores and changes from baseline in IBDQ at Week 8 and Week 16 per intervention treatment group.
- Reduction relative to baseline of infiltrate/histopathology (rectal/sigmoidal biopsies) using the Robarts Histopathology Index (RHI), the Geboes and Nancy Histology Scoring Scales at Week 8 and Week 16 (if available) per intervention/treatment group.

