9.2. Efficacy Analysis

Analysis of efficacy data will be carried out in the Full Analysis Set in which subjects who prematurely discontinue the study due to adverse reaction(s) will be considered treatment failures.

The primary efficacy endpoint of the study is the change in the Modified Mayo Score (MMS) from Baseline to Week 8. This change will be compared between subjects who received ABX464 and placebo for each ABX464 treatment arm separately using an ANCOVA model adjusting for randomized study treatment arm, previous biological or JAK inhibitors treatment use (i.e. randomization strata), and baseline MMS.

The dose testing will commence with comparing the ABX464 50mg dose with placebo. If this is significant at a 5% two-sided level (i.e. $p < 0.05$) a comparison against placebo will be carried out at the ABX464 100mg dose. Again, if significance at a 5% level for this test is observed the procedure will be repeated at the ABX464 25mg dose. In this closed procedure no adjustment for multiple comparison is needed. Should the data warrant it, testing between doses may also be conducted.

In addition, descriptive statistics will be presented by treatment arm for all secondary efficacy variables for each measurement timepoint.

These statistics include:

- Continuous variables: mean, standard deviation, minimum and maximum, 95%
- Confidence intervals for the mean, median and quartiles will be presented.
- Categorical variables: counts, rates and 95% confidence intervals for the rates will be calculated.

In addition to descriptive statistics, the following analyses will also be carried out for the variables indicated below:

- The global (combined) ABX464 treatment effect vs. placebo in the change from Baseline in Modified Mayo Score at Week 8
- The proportion of subjects with clinical remission at Week 8 will be compared across study treatment arms using a stratified Mantel-Haenszel test.
- Mixed model analysis of covariance will be conducted for the following measurements:
 - The change from baseline in microRNA-124 levels in total blood (PAXgene®) at Week 1, Week 4, Week 8 and Week 16 and in tissue (RNA later).
 - The change from baseline in fecal calprotectin levels at Week 8 and Week 16.
 - The change from screening in the histopathology/infiltrate (rectal/sigmoidal biopsies) assessed by the Robarts Histopathology Index, the Geboes and Nancy Histology Scoring Scales at Week 8 and Week 16 (if available).

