9.4. Determination of Sample Size

The primary endpoint is the change in the Modified Mayo Score (MMS) from Baseline to Week 8. The primary endpoint will be compared between subjects who received ABX464 and placebo for each ABX464 treatment arm separately.

For the sample size calculation, the following assumptions were made:

- mean reduction in MMS (ABX464): 2.5
- mean reduction in MMS (placebo): 1.0
- pooled standard deviation of reduction in MMS: 2.1
- Type 1 error: 5% two-sided.
- Treatment testing to use a sequential, gate-keeping strategy, where treatment arms will be tested in the following order: ABX464 50mg vs. placebo, ABX464 100mg vs. placebo, ABX464 25mg vs. placebo. Subsequent tests will only be performed only if prior test(s) are significant ($p<0.05$).
- >90% power
- Two-sample t-test
- 5% dropout rate prior to Week 8 MMS assessment (all treatment arms)
- 1:1:1:1 (ABX464 100mg: ABX464 50mg: ABX464 25mg: placebo) study treatment arm allocation ratio.

If the above assumptions hold true, then a total sample size of 232 subjects will be required to be randomized (58 subjects randomized to each study treatment arm).

Due to the SARS Cov-2 pandemic the drop-out rate of the study is expected to be somewhat higher than originally estimated. Therefore, an additional 12 subjects are planned to be recruited in the study leading to an overall sample size of 244 patients (61 subjects randomized to each study treatment arm).

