15.1.3. PRIMARY ANALYSIS OF PRIMARY EFFICACY VARIABLE

The primary efficacy analysis will be performed for FAS and PPAS.

The primary objective of this study is to determine an optimal ABX464 dose to be used in moderate to severe active ulcerative colitis patients who have failed or are intolerant to immunomodulators, Anti-TNF α , vedolizumab, JAK inhibitors and/or corticosteroids by comparing the mean change from baseline in the MMS at Week 8 for the three ABX464 dose levels to the placebo. An analysis of covariance (ANCOVA) model will be used to assess these changes.

The ANCOVA model for Change from Baseline MMS at Week 8 will include the fixed treatment effect, the previous use of biological or JAK inhibitors effect and the covariate, baseline MMS and a random error term.

The assumptions that the random errors in the ANCOVA model are normally distributed with homogeneity of variances will be checked. If either the hypothesis regarding normality of errors or the hypothesis of equal variances is rejected at the 5% significance level a nonparametric ANCOVA using the ranked data will be performed to test for differences in the mean change from baseline. The least square means and confidence intervals from the parametric ANCOVA will also be presented.

The dose testing will commence with comparing the ABX464 50mg dose with placebo. If this is significant at a 5% two-sided level (i.e. $p < 0.05$) a comparison against placebo will be carried out at the ABX464 100mg dose. Again, if significance at a 5% level for this test is observed the procedure will be repeated at the ABX464 25mg dose. If in this sequence of comparisons of ABX464 dose levels to placebo one is not significant (i.e., $p \geq 0.05$) the additional comparisons to placebo will not be

Document: \\iedc-vnasc01\BIOSdata\Abivax\ABX464\FZA92720\Biostatistics\Documentation\SAP\ABX464-103_SAP_V2.0_10MAY2021

Author: [REDACTED]

Version Number:
Version Date:

2.0
10May2021

Template No.: CS_TP_BS016 Revision 5

Reference: CS_WI_BS005

Effective Date: 01Apr2018

performed. Should any of these comparisons with the placebo treatment group be significant, further exploratory testing of the dose groups against each other will be conducted at the same significance level. A global comparison of all active treatment groups vs placebo group will also be conducted.

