15.2.1. SECONDARY EFFICACY VARIABLES & DERIVATIONS

15.2.1.1. Number and Percentage of Patients in Clinical Remission at Week 8 and Week 16

Clinical remission is defined as:

- A stool frequency subscore = 0 or 1
- A rectal bleeding sub-score = 0
- An endoscopy sub-score = 0 or 1 (modified to exclude friability)

This endpoint will be calculated per treatment arm and presented descriptively.

Percentage of patients in clinical remission at Week 8

$$= \frac{\text{Number of patients in treatment arm with clinical remission at Week 8}}{\text{Total number of patients in the treatment arm}} \times 100$$

Percentage of patients in clinical remission at Week 16

$$= \frac{\text{Number of patients in treatment arm with clinical remission at Week 16}}{\text{Total number of patients in the treatment arm at Week 16}} \times 100$$

Percentage of patients in clinical remission at Week 8 or Week 16

$$= \frac{\text{Number of patients in treatment arm with clinical remission at Week 8 or Week 16}}{\text{Total number of patients in the treatment arm at Week 8 or Week 16}} \times 100$$

Number of patients with clinical remission at week8 and not at week 16 as well as number of patients with clinical Remission at Week 16 and not at Week 8 will also be presented.

Document: \\ieddc-vnasc01\BIOSdata\Abivax\ABX464\FZA92720\Biostatistics\Documentation\SAP\ABX464-103_SAP_V2.0_10MAY2021

Author: [REDACTED]

Version Number: 2.0
Version Date: 10May2021

Template No.: CS_TP_BS016 Revision 5

Reference: CS_WI_BS005

Effective Date: 01Apr2018

15.2.1.2. Combined Number and Percentage of Patients in Clinical Remission at Week 8 and Week 16

Clinical remission is defined in Section 15.2.1.1. The number and percentage of patients in clinical remission at both Week 8 and Week 16 will be summarized by treatment arm.

Percentage of patients in clinical remission at Week 8 and Week 16

$$= \frac{\text{Number of patients in treatment arm with clinical remission at Week 8 and Week 16}}{\text{Total number of patients in the treatment arm at both visits}} \times 100$$

15.2.1.3. Number and Percentage of Patients with Clinical Response at Week 8 and Week 16

Clinical response is defined as

- A reduction from baseline in MMS ≥ 2 points, and
- A reduction in MMS $\geq 30\%$ from baseline with a decrease in rectal bleeding sub-score ≥ 1 point or absolute rectal bleeding sub-score ≤ 1 point

This endpoint will be summarized by treatment arm.

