The proportion of patients with clinical remission at Week 8 will be compared across study treatment arms using a stratified Mantel-Haenszel test to estimate the common odds ratio for each active arm vs placebo, with exposure to previous biological or JAK inhibitors as the stratification factor. As the common odds ratio is calculated under the assumption that the underlying odds ratio is homogeneous across the strata, the hypothesis of homogeneity of the odds ratio across strata will be tested using the Breslow-Day test. The chi-square, degrees of freedom and corresponding p-value for the Breslow-Day test for homogeneity of the odds ratios will be presented. A p-value less than 5% will indicate that the assumption of a common odds ratio is unreasonable. In this case, the Cochran-Mantel-Haenszel estimate of the common odds ratio will not be reported, but rather the strata-specific (i.e. previous exposure to biological or JAK inhibitors) estimates of the odds ratio.

If a sample size is too small for the hypothesis of homogeneity of the odds ratio to be tested by the Breslow-Day test, the stratum -specific or unstratified odds ratio will be determined.

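### The only visible planned test of Week 8 clinical remission leaves out baseline MMS, a probably prognostic value the SAP adjusts for elsewhere; the test is valid but gives up modest efficiency

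*SAP*

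**What the plan says.** Protocol 9.2 plans that "The proportion of subjects with clinical remission at Week 8 will be compared across study treatment arms using a stratified Mantel-Haenszel test". SAP 15.2.3.2 gives the detail: the method estimates "the common odds ratio for each active arm vs placebo, with exposure to previous biological or JAK inhibitors as the stratification factor". A Breslow-Day test then decides whether a common odds ratio is reported. If the sample is too small for that test, stratum-specific or unstratified odds ratios are used instead.

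Remission is defined in Protocol 2.4 as "stool frequency subscore = 0 or 1 and rectal bleeding subscore = 0 and endoscopy subscore = 0 or 1".

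Elsewhere the SAP does use baseline MMS. The primary ANCOVA in 15.1.3 contains treatment, "the previous use of biological or JAK inhibitors effect and the covariate, baseline MMS and a random error term". SAP 15.2.3.1 applies that same procedure to clinical response, the endoscopic outcomes, mucosal healing and remission at Weeks 8 and 16 combined. Week 8 remission alone is not on that list. The baseline MMS subgroups of SAP 7.5 are used in 15.1.4.2 for the primary endpoint only. Randomization (SAP 7.2) is stratified by prior exposure and US/non-US site, not by MMS.

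**The concern.** Remission is a fixed threshold at Week 8, while patients enter across MMS 5 to 9 (or 4, for some enrolled under the original protocol). How far a patient must improve therefore depends on where that patient starts. Neither the randomization nor the visible remission analysis takes this into account, and the SAP gives no reason for treating Week 8 remission differently from its neighbours.

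Week 8 remission is the first-listed secondary endpoint, and the trial is meant to support a choice of dose. At stake are some efficiency in each dose-versus-placebo comparison and protection against a chance difference in baseline severity between arms.

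**Working it through.** **1. The plan's own figure.** No power is stated for remission. The sample size rests on the MMS change: reductions of 2.5 and 1.0, "pooled standard deviation of reduction in MMS: 2.1", 5% two-sided. For 90% power, n = 2 × (1.960 + 1.282)² × 2.1² / 1.5² = 41.2, so 42 per arm, or 45 after 5% dropout. The stated 58 per arm leaves 58 × 0.95 ≈ 55 evaluable. Power is Φ(1.5 / (2.1 × √(2/55)) − 1.96) = Φ(1.79) ≈ 96%, so the claim of more than 90% is met. The final size is 61 per arm.

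**2. Fall needed to remit.** The highest MMS compatible with remission is 1 + 0 + 1 = 2. The minimum fall is therefore 5 − 2 = 3 from MMS 5 (4 if the stool sub-score is already 0) and 9 − 2 = 7 from MMS 9.

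**3. Is MMS plausibly prognostic?** The documents give no observed association. Taking the sample-size figures as normal, with a 0.5 continuity correction and a reduction that does not depend on baseline, P(MMS ≤ 2) = 1 − Φ((baseline − 2.5 − mean reduction) / 2.1):

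| | MMS 5 | MMS 9 |
|---|---|---|
| ABX464 (mean 2.5) | 1 − Φ(0) = 50.0% | 1 − Φ(1.90) = 2.8% |
| Placebo (mean 1.0) | 1 − Φ(0.71) = 23.8% | 1 − Φ(2.62) = 0.4% |

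If the reduction is instead proportional to baseline, the ABX464 values run from 36% to 6%. Dividing the change in log odds by 4 points gives a slope of about −0.9 (ABX464) or −1.1 (placebo) in the table, and about −0.5 from 36% and 6%. These figures only approximate remission, because an MMS of 2 that includes bleeding is not remission.

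**4. Effect of adding baseline MMS.** First simulation: 61 per arm, 8,000 trials per row. Assumed, not in the documents: baseline MMS with mean 6.85 and SD 1.19; half the patients previously exposed, with odds ratio 0.6. The 35.0% versus 11.1% rates are the phase IIa rates in Protocol 1.3.

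| Remission rates | Odds ratio per MMS point | Power, planned test | Power, logistic (score test) | SD of log odds ratio, planned / adjusted |
|---|---|---|---|---|
| 35% vs 11.1% | 1.0 | 90.2% | 90.3% | 0.543 / 0.551 |
| | 0.65 | 89.8% | 91.0% | 0.548 / 0.571 |
| | 0.5 | 90.0% | 92.8% | 0.537 / 0.586 |
| 25% vs 11.1% | 1.0 | 51.8% | 52.7% | 0.554 / 0.564 |
| | 0.65 | 52.6% | 54.5% | 0.549 / 0.570 |
| | 0.5 | 52.4% | 56.8% | 0.554 / 0.594 |

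The variance of a standardised risk difference ran from about 1% higher with adjustment (no slope) to about 8% lower. With equal rates of 15%, the planned test rejected in 4.7 to 5.1% of trials.

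An odds ratio of 0.5 per point is a slope of only ln 0.5 = −0.69. A second simulation, at 30% versus 11.1% and reaching steeper slopes, gave the logistic model a gain of about 1 to 8 power points by the likelihood-ratio test. Part of that came from a slightly liberal test (type I error 5.4 to 5.8%). Risk-difference variance changed by +1% to −15%.

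**5. Chance imbalance.** One SD of the arm difference in mean baseline MMS is 1.19 × √(2/61) ≈ 0.22 points. At odds ratios of 0.8 to 0.5 per point, an imbalance of that size moves the Mantel-Haenszel log odds ratio by 0.05 to 0.15, a factor of 1.05 to 1.16. It moves the risk difference by 0.6 to 2.1 percentage points, against almost nothing after adjustment.

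**6. Splitting the Mantel-Haenszel test by MMS category as well.** Four strata gained about 0 to 5 power points. In about 60 to 68% of trials at least one stratum had no placebo remitter, against 7 to 8% with the planned two strata.

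**The case against.** The strongest case against is that nothing here is wrong. Randomization makes the planned test valid, its type I error is about 5%, and chance imbalance is not bias. Its stratification factor matches one of the randomization factors. Remission lies outside the gatekept dose sequence, and Protocol 9.2 closes its additional analyses by calling the p-values descriptive. The slope and the baseline MMS distribution are assumed. All of this stands, and it makes the point one of efficiency and consistency.

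Two further objections also stand. A reader might infer that omitting MMS makes the odds ratio less precise. It does not: in every row above the SD of the log odds ratio is slightly larger after adjustment, because the adjusted odds ratio is a conditional, more extreme quantity. The gain appears in power and in the risk difference. And a reader might take the obvious remedy to be extra Mantel-Haenszel strata. The sparse cells in step 6 would often trigger the small-sample rule in SAP 15.2.3.2, which can end in an unstratified odds ratio.

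What the objections do not explain is why Week 8 remission is handled differently from clinical response and combined remission. Descriptive p-values do not remove the value of an estimate that resists imbalance when doses are being compared.

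**Conclusion.** The point holds as a modest improvement. The visible test of Week 8 remission omits a collected baseline value that the SAP uses for its primary endpoint and, read literally, for most other binary secondary endpoints. The likely cost is roughly 0 to 8 points of power and 0 to 15% of risk-difference variance, with the larger figures needing the steep end of the assumed slopes. If baseline MMS is not prognostic, adjustment gains nothing or costs about 1% of variance. Chance imbalance in severity passes into the estimate.

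Three stronger readings are not supported:

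- That the test is invalid or biased: it is neither.
- That baseline MMS is shown to predict remission: the threshold makes this likely, but neither document reports it.
- That no other test of Week 8 remission exists: redacted lines close SAP 15.2.3.1, so only the visible text can be judged.

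**What to change.** In SAP 15.2.3.2, add a logistic regression of Week 8 remission on treatment, prior biologic/JAK exposure and baseline MMS as a continuous covariate. Report the standardised risk difference with its 95% confidence interval beside the adjusted odds ratio for each dose versus placebo. Keep the exposure-stratified Mantel-Haenszel test, with its Breslow-Day rule, as supportive. Do not split it into four strata. Under Protocol section 9, an SAP amendment must be documented and signed before final database lock.

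The cost is a short paragraph and one extra model to program; baseline MMS is already in the covariate list of SAP 7.1. There are two drawbacks. The adjusted odds ratio is conditional and not directly comparable with the Mantel-Haenszel one, which the text should say. The likelihood-ratio test is slightly liberal at this sample size (about 5.4 to 5.8%); the score test came out at 4.9 to 5.3% in the first simulation, so the SAP should name which is used.

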15.2.3.3. Analysis of Secondary Variables Measured Repeatedly Over Time

In addition to descriptive statistics as described in Section 15.2, mixed model repeated measures ANCOVA will be used to assess the following secondary variables:

- Change from screening in MMS to Week 8 and Week 16 and change from baseline to all post-baseline visits in pMMS during the study, by treatment group vs placebo group.
- The change from baseline in fecal calprotectin levels at Week 8 and Week 16.
- The change from screening in the histopathology/infiltrate (rectal biopsies) assessed by the Robarts Histopathology Index, the Geboes and Nancy Histology Scoring Scales at Week 8 and Week 16 (if available).

Mixed Model for Repeated Measures (MMRM) will be used to analyze change from baseline in MMS, pMMS, fecal calprotectin, RHI, Geboes and Nancy scores. Change from baseline at the specified Week

Document: \\ieedc-vnasc01\BIOSdata\Abivax\ABX464\FZA92720\Biostatistics\Documentation\SAP\ABX464-103_SAP_V2.0_10MAY2021

Author: [REDACTED]

Version Number: 2.0
Version Date: 10May2021

Template No.: CS_TP_BS016 Revision 5

Reference: CS_WI_BS005

Effective Date: 01Apr2018

will be analyzed by using a MMRM model with baseline value as a covariate, fixed effects for treatment group, exposure to previous biologics or JAK inhibitors, visit, visit by treatment group interaction and a random error term. For the MMRM model, the Kenward-Roger method for approximating the denominator degrees of freedom and correcting for bias in the estimated variance-covariance of the fixed effects will be used. This will be achieved by specifying the DDFM = KR option in the MODEL statement within PROC MIXED. An unstructured covariance will be selected initially, and if convergence is not achieved with this structure, the following covariance structures will be used in the order listed until convergence is achieved: Toeplitz (TOEP), Autoregressive (AR) and Compound Symmetry (CS).

The strata US vs non-US sites will not be included as a factor in the model as the stratification occurs only because US patients will not receive 100 mg dose of ABX464.

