5.2.4. Day 57 and Day 113 Visits

- IBD Questionnaire (as the first visit procedure);
- Physical examination and vital signs;
- Body weight;
- At Day 113, population Pharmacokinetics blood samples at either pre-dose, 1, 2, 4h and if possible 48 h (Day 115 only) or pre-dose, 0.5, 1.5, 3h and if possible 48 (Day 115 only);
- Hematology and Biochemistry including blood pregnancy test for all women of childbearing potential, coagulation parameters and troponin;
- Blood sample for miR-124 dosage (PAXgene® tube) and cytokines determination;
- 12-leads ECG;
- Fecal calprotectin;
- Sigmoidoscopy with rectal/sigmoidal biopsies (Day 113 endoscopy is conditional on the response at Day 57);
- Modified Mayo Score at Day 57 (and Day 113 if available; OR pMMS at Day 113 if Day113 endoscopy not performed);
- Check treatment compliance;
- Adverse Events reporting;
- Study treatment dispensation at Day 57 visit;
- Review the patient e-Diary;
- At Day 113, enrolment of patients willing to take part to the maintenance phase;
- Schedule next patient visits.

5.2.5. End of Study Visit (Within a week after last dose \pm 2 days)

This EoS visit applies to all premature discontinued patients and to patients not taking part to the maintenance study. Patients will perform an End of Study Visit (EoS) within a Week after last dosing (i.e D120 \pm 2 days if the patient completed the study and is not taking part in maintenance study). Patients will be treated according to the standard of care from the last day of study treatment.

Following examinations/procedures should be performed:

- Physical examination and vital signs;
- Body weight;
- Hematology and Biochemistry and a follow-up 3 Weeks later;
- Partial Modified Mayo Score;
- 12 leads ECG;
- Fecal calprotectin;
- Adverse Events reporting.

NB#1: In case of premature discontinuation occurring during the treatment phase (D1-D113), the above examinations should be performed as an End of Study Visit 7 days \pm 2 days after last dose.

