5.3.7. Sigmoidoscopy with rectal/sigmoidal biopsies

Sigmoidoscopies procedures (or colonoscopies if applicable) will be standardized for optimized video acquisition at clinical sites. Sigmoidoscopies should be performed according to the Central Imaging Management System Charter.

Central Imaging Management System will be provided including a central image database. Once uploaded, video data will be analyzed for quality and resolution prior to independent review by an expert central reader.

Study videos will be scored separately using the Mayo Clinic Score (excluding friability) for all time points by central readers who are blinded to the treatment and visit sequence of the recordings.

The central reader's score at Screening, Day 57 and Day 113 (if available) will be entered directly into the eCRF. Screening videos will be evaluated for eligibility and scores communicated to sites within four (4) business days. All procedure videos collected for outcome evaluation will be scored and results communicated within five (5) business days.

Two rectal biopsies (plus optionally two sigmoidal biopsies, if the inflammation of the sigmoid is observed) will be performed at Screening, at Day 57 and at Day 113 (if applicable). The two (or 4) biopsies will be sent to central laboratories for assessment according to Robarts Histopathology Index (RHI), the Geboes and Nancy Histology Scoring Scales (please refer to the lab manual) and for miRNA-124 determination (RNA later).

RHI score ranges from 0 (no disease activity) to 33 (severe disease activity) and is based on the evaluation of four main parameters: chronic inflammatory infiltrate, lamina propria neutrophils and eosinophils, neutrophils in the epithelium and erosion/ulceration. Overall, this histological index has been reported to be reproducible, responsive and valid and will be used for confirmation of the mucosal healing. The patient's biopsies will be also read according to the Geboes and Nancy Histology Scoring Scales for completeness purposes.

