Flexible sigmoidoscopy with rectal and/or sigmoidal biopsies will be performed at screening, at Day 57 +/- 4 days (Week 8) and at Day 113 +/- 4 days (Week 16). The Day 113 measurement will only be taken if the patient does not experience endoscopic improvement (i.e. endoscopy sub-score of 2 or 3) at Day 57. In the event of clinical progression of the disease after Week 8, defined as at least a 2-point increase from screening in pMMS, with a MMS ≥ 4 confirmed by an endoscopy sub score of 2 points or higher, the patient will exit the study.

Study Design

Document: \\ieedc-vnasc01\BIOSdata\Abivax\ABX464\FZA92720\Biostatistics\Documentation\SAP\ABX464-103_SAP_V2.0_10MAY2021

Author: [REDACTED]

Version Number: 2.0
Version Date: 10May2021

Template No.: CS_TP_BS016 Revision 5

Reference: CS_WI_BS005

Effective Date: 01Apr2018

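### The planned Week 16 RHI, Geboes and Nancy contrasts can be biased, usually towards no effect, because the Week 8 endoscopy sub-score decides who is biopsied and is not in the models

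*SAP*

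**What the plan says.** **Who is assessed at Week 16.** SAP section 3.1: "The Day 113 measurement will only be taken if the patient does not experience endoscopic improvement", where lack of improvement means a Day 57 endoscopy sub-score of 2 or 3. Protocol section 5.2.4 agrees: "Day 113 endoscopy is conditional on the response at Day 57". The biopsies follow the endoscopy; under Protocol section 5.3.7 they "will be performed at Screening, at Day 57 and at Day 113 (if applicable".

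**How Week 16 is analysed.** SAP section 15.2.3.3 lists "The change from screening in the histopathology/infiltrate (rectal biopsies) assessed by the Robarts Histopathology Index" among its repeatedly measured outcomes, and says the repeated-measures model "will be used to analyze change from baseline in MMS, pMMS, fecal calprotectin, RHI, Geboes and Nancy scores". Its terms are "baseline value as a covariate, fixed effects for treatment group, exposure to previous biologics or JAK inhibitors, visit, visit by treatment group interaction", plus an error term. "An unstructured covariance will be selected initially", with simpler structures only if the model does not converge. The Week 8 endoscopy sub-score is not among these terms, nor in the covariate list of SAP section 7.1.

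**What is said about missing values.** SAP section 7.3 gives imputation rules for MMS components at Week 8 only, and section 15.2.2 refers back to it. Neither covers a Week 16 biopsy that was not taken. The estimand table in SAP section 2.3 has no row for histology or for Week 16 MMS. The Week 16 histology analyses carry only an if-available remark.

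**The concern.** A likelihood-based repeated-measures model gives valid estimates when, given the data in the model, missingness carries no further information about the missing values. The SAP does not state this assumption, but the method relies on it. Here the variable that decides missingness is known and recorded, but it is absent from the three histology models, which see only baseline and Week 8 histology plus arm, prior exposure and visit.

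If the drug improves endoscopy by Week 8, more active than placebo patients are skipped. Among patients with the same Week 8 histology, those skipped have the better endoscopy. If better Week 8 endoscopy also predicts better Week 16 histology, the model predicts too poor a Week 16 score for the skipped patients, and does so more often on active drug. The contrast with placebo then shrinks. Week 16 histology by dose versus placebo is a listed secondary objective (Protocol section 2.2).

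**Working it through.** **The plan's own figures.** The documents give no figure for the Week 16 models. The nearest is the sample size in Protocol section 9.4. It reproduces: 58 × 0.95 ≈ 55 evaluable per arm gives 96.0% power per comparison and about 90.8% for all three ordered tests, consistent with the stated target above 90%. It concerns Week 8 MMS and does not bear on this point.

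**Step 1: how many would be skipped.** Inputs are 61 per arm and 5% dropout before Week 8 (Protocol section 9.4), and phase IIa endoscopic improvement of 50.0% versus 11.1% (Protocol section 1.3).

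- Reaching Week 8: 61 × 0.95 ≈ 58 per arm.
- Skipped on active: 58 × 0.50 = 29.
- Skipped on placebo: 58 × 0.111 ≈ 6.

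These rates come from 32 randomised patients, so other rates are tried below.

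**Step 2: what the planned model estimates.** With Week 8 complete and Week 16 missing for some, the unstructured model's Week 16 contrast is

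b(arm) + b(H8) × [mean H8 active − mean H8 placebo],

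where H8 is Week 8 histology. The coefficients come from regressing Week 16 histology on arm and H8 in re-scoped patients; the means are over all patients. Baseline and prior exposure were left out of this check.

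**Step 3: what drives the bias.** The key quantity is the partial correlation of Week 8 endoscopy (E8) with Week 16 histology (H16), given H8:

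[r(E8,H16) − r(E8,H8) × r(H8,H16)] / √[(1 − r(E8,H8)²)(1 − r(H8,H16)²)].

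All correlations are assumptions. With r(E8,H8) = 0.5 and r(H8,H16) = 0.6:

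- r(E8,H16) = 0.30: 0/√(0.75 × 0.64) = 0.
- r(E8,H16) = 0.40: 0.10/0.693 = 0.14.
- r(E8,H16) = 0.50: 0.20/0.693 = 0.29.

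Swapping 0.5 and 0.6 gives the same three values.

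**Step 4: results.** Large-sample simulation in within-arm SD units, with an assumed true Week 16 contrast of −0.50. Positive bias is against the drug; percentages are bias divided by 0.50.

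| Improvers, active vs placebo | Partial 0 | Partial 0.14 | Partial 0.29 |
|---|---|---|---|
| 50% vs 11.1% | 0.00 | +0.06 to +0.07 (12–14%) | +0.13 to +0.14 (26–28%) |
| 40% vs 15% | 0.00 | +0.04 (8%) | +0.08 (about 17%) |
| 30% vs 20% | 0.00 | +0.02 (3–4%) | +0.03 to +0.04 (6–7%) |
| 50% vs 50% | 0.00 | 0.00 | 0.00 |

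The bias vanishes when endoscopy adds nothing beyond histology, and in these runs also when skip rates are equal.

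**Step 5: a bounded score.** RHI runs from 0 to 33 (Protocol section 5.3.7), so improvers may sit at the floor. In an assumed latent-inflammation model with 21% placebo and 37–48% active improvers, the planned contrast was 7–11% too small with no floor. With a floor it ranged from about 9% too small to 2% too large.

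**Step 6: MMS.** Week 8 MMS already includes the endoscopy sub-score as one of three summed components. Simulated bias ran from −0.19 to +0.09 points on true contrasts of about −1.3 to −2.0, so even its sign depends on the assumed correlations.

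**The case against.** The best defence is that the model is less naive than it looks. With an unstructured covariance, each skipped patient's Week 16 value is informed by that patient's own baseline and Week 8 histology. If histology carries all the relevant information, nothing is lost. The documents give no correlation that shows otherwise. This stands: a reader might infer that the Week 16 contrasts are biased, but the documents support only that they can be.

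A reader might also extend the point to Week 16 MMS. That is not supported, because the sub-score is inside the Week 8 total and the direction is undetermined.

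Importance is limited. Protocol section 9.2 treats mixed-model p-values as descriptive. Histology is not among the estimands in SAP section 2.3. The Week 8 primary analysis, pMMS and fecal calprotectin do not depend on the skip rule. The worst bias in the table, 0.14 SD, is below one standard error of a complete-data contrast with 61 per arm, √(2/61) = 0.18 SD before baseline adjustment. All of this limits severity. It does not say what the Week 16 contrast estimates or justify leaving out a recorded variable that decides missingness.

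Finally, imputation with the sub-score is no complete repair. No patient with sub-score 0 or 1 has a Week 16 biopsy, so any model extrapolates from sub-scores 2 and 3. With a floor, unbounded linear imputation overstated the effect by 6–22% in the latent model; imputation kept within the score's range stayed within about 5%. This objection stands and shapes the fix. The planned model makes the same extrapolation without the sub-score and without saying so.

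**Conclusion.** The point holds for RHI, Geboes and Nancy. The Week 16 contrasts can be biased, usually towards no effect, and the plan neither defines the target nor tests the assumption.

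The documents cannot fix the size. It is about zero if Week 8 endoscopy adds nothing beyond Week 8 histology, and roughly 5–15% of the contrast under plausible assumed correlations and skip rates. If the phase IIa rates recur it could reach 12–28% at the partial correlations tried. The percentages rest on an assumed true contrast of 0.50 SD, and a score floor can reduce or slightly reverse the bias.

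The change should be made, but the point does not threaten the trial's main conclusion.

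**What to change.** 1. State in the SAP whether the Week 16 histology contrast is for all patients or only for Week 8 endoscopic non-improvers.
2. If for all patients, multiply impute the Week 16 values skipped by design. Use arm, baseline, prior exposure, Week 8 histology, the Week 8 endoscopy sub-score, and pMMS at Weeks 8 and 16. pMMS is scheduled at Day 113 even when endoscopy is skipped (Protocol section 5.2.4).
3. Keep imputed values within each score's range.
4. Keep the sub-score out of the model that compares the arms, because it is measured after randomisation.
5. Add a delta or tipping-point analysis for the skipped patients, since their values rest on extrapolation.
6. Label Week 16 by-arm summaries of re-scoped patients as not comparable between arms.

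This needs SAP text and some programming, with no new data. Week 16 intervals will be wider.
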